6.2 Measures of outcome

The principal clinical outcome measure is:

• all new low-energy fractures (other than face or skull) or clinical, radiologicallysupported, vertebral fractures reported.

Any apparent differences in fracture rates will be explored by subdivision into: proximal femoral, other lower limb/pelvis, distal forearm, other arm, clinical vertebral, and other fractures.

Other secondary outcome measures are:

- New radiologically-confirmed fractures
- Death after trial entry; the possible link between death and fracture will be examined in analyses of deaths occurring within three months of a new fracture
- General health status as measured by SF-12 and EQ-5D
- Hospital admissions after trial entry (number, length, place, and association with fracture)
- Change of residence category
- Falls (within five one-week window periods)
- Possible adverse effects (e.g. renal stones, gastrointestinal symptoms)
- New cancer registrations (Total, colon, breast, other)
- Deaths attributed to cardiovascular or cerebrovascular disease
- New cases of diabetes, taking oral hypoglycaemics and/or insulin

The ways in which these data will be displayed in the final report are illustrated in Appendix 11.

It is anticipated that other variables, such as bone density, genetic polymorphisms, and balance will be measured in explanatory studies and these will be described in separate protocols.

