4.3 Four monthly postal contact

Each fresh supply of materials will contain a brief form for completion by the participant (Appendix 8). This has the following purposes:

- i) confirmation that the materials arrived safely
- ii) collection of information about the preceding four months: any new fracture; any admission to hospital; and any change in residence
- iii) details of tablet compliance from the preceding week: whether the tablets have been taken, how often, and reason for stopping if applicable.

As a further measure of compliance, a five percent randomly selected subsample of recruits will be asked to return all unused supplies for a tablet count. A detailed protocol is provided in Appendix 9.

4.4 Additional information sought by post at four, twelve, twenty-four, thirtysix and forty-eight months after entry

Longer forms will be sent at four, twelve, twenty-four, thirty-six and forty-eight months (Appendix 10) which, in addition to the above, will collect the following information:

- i) falls in last week
- ii) the EQ-5 questionnaire
- iii) the SF-12 questionnaire
- iv) Diabetic or not, use of oral hypoglycaemics and/or insulin

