4.5 Notifications by general practitioners

Stickers and the information sheet will ask the general practitioner to notify the Trial Office by phone if the participant:

- (i) sustains a new fracture
- (ii) moves to another practice

- (iii) has a suspected adverse event related to the trial, specifically developing renal insufficiency (creatinine greater than 250 micromols per l), renal stones, or hypercalcaemia (based on local reference standards)
- (iv) develops diabetes mellitus requiring oral hypoglycaemics and/or insulin.
- (v) dies (and cause of death)

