The incidence of adverse effects from the proposed dosage of vitamin D and calcium is anticipated to be very low - in the systematic review renal insufficiency or stones were reported for 4/4025 (0.1%) and gastro-intestinal disturbances for 93/3892 (2.4%).

Collaborators and participants may write to the chairman of the steering committee about any worries they may have about the trial. If concerns arise about particular side-effects or about particular types of participants, these will be relayed to the Chairman of the Data Monitoring Committee.

If clinically indicated, rapid unblinding of trial materials will be available through the trial office.

The Multicentre Research Ethics Committee for Scotland has approved the trial. The trial will be conducted according to the MRC Good Clinical Practice Guidelines (1998)²².

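### Gastrointestinal symptoms are a named secondary outcome, but no data source described in the protocol asks all participants about them

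*Protocol*

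**What the plan says.** Section 6.2 includes among the secondary outcomes "Possible adverse effects (e.g. renal stones, gastrointestinal symptoms". In section 8.3 the sponsor cites its systematic review: gastrointestinal disturbance in 93/3892 (2.4%), renal insufficiency or stones in 4/4025 (0.1%).

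The collection sections describe these sources:

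- **Four-monthly form (4.3).** Its event content is "collection of information about the preceding four months: any new fracture; any admission to hospital; and any change in residence". Its tablet content is "details of tablet compliance from the preceding week: whether the tablets have been taken, how often, and reason for stopping if applicable".
- **Longer forms (4.4).** These are forms "which, in addition to the above, will collect the following information": falls in the last week, EQ-5D, SF-12 and diabetes status.
- **General practitioner (4.5).** Notification is asked for if the participant "has a suspected adverse event related to the trial, specifically developing renal insufficiency", renal stones or hypercalcaemia. New fracture, change of practice, treated diabetes and death are also notified.
- **Best contact (4.6).** Fracture, residence, admission, serious illness or death, and tablet delivery problems.
- **Study nurse (4.2, 8.1).** One scheduled contact at two weeks, later ones when judged necessary, to check residence and whether there are problems with the tablets. No record of the answers is described.
- **National flagging (4.8).** Death and cancer.
- **Clinical co-ordinator (8.1).** Unexpected events that might be related to participation.

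**The concern.** An outcome compared between randomised groups needs a source that looks for it in the same way in everyone. Renal stones, the other example in section 6.2, have a named route through the general practitioner. Falls and diabetes have form items. Gastrointestinal symptoms have neither, although the protocol expects them more often than the renal events.

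The one routine field that can hold them depends on having stopped tablets. A participant who has symptoms and carries on would usually count as event-free. The quantity observed then combines the symptom with the decision to stop. Section 6.1 bases analyses on everyone randomised whatever their tablet taking, and an outcome observable mainly through stopping fits that poorly.

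What is at stake is the tolerability comparison, chiefly on the calcium margin. Section 1.3 gives possible hazards as part of the reason for the trial. Later analysis cannot recover symptoms that were never recorded, so this is not something a statistical analysis plan could settle.

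**Working it through.** **1. Sources against outcome.** None of the seven sources above is described as having a gastrointestinal or general symptom item. Four could reveal some cases: the reason for stopping (routine and recorded), the two-week nurse check (universal, but no recording described), hospital admissions (severe cases only) and ad hoc reports from best contacts or co-ordinators. Co-ordinators report unexpected events, whereas section 8.3 treats gastrointestinal disturbance as expected.

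**2. The plan's own figures.** 93/3892 = 2.39% and 4/4025 = 0.10%, as stated. For the section 7.1 sample size (15% v 12%, two-sided 0.05, 80% power):

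n per side = [1.96√(2 × 0.135 × 0.865) + 0.842√(0.15 × 0.85 + 0.12 × 0.88)]² / 0.03² = 2,036, so 4,072 in total against the stated 4,000. Power at 2,000 per side is 79.3%. Both agree with the protocol; the point disputes no stated figure.

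**3. What partial capture does.** Let p0 and p1 be the true risks without and with calcium, and c the share of symptomatic people recorded.

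- Equal capture: the visible difference is c(p1 − p0) and the visible ratio is cp1/cp0 = p1/p0. The difference shrinks and the ratio stays.
- Unequal capture can bias either way. With true risks of 2.4% v 3.6% and capture of 75% v 50%, the visible risks are 1.8% v 1.8%, so a real excess disappears. With true risks of 2.4% in both and capture of 25% v 50%, they are 0.6% v 1.2%, a false doubling.

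**4. Illustrative power, equal capture.** Assumptions: p0 = 2.4% (the review figure, used here as the fully ascertained risk without calcium, which the protocol does not say it is), p1 = 3.6% (relative risk 1.5), and the values of c. The first column assumes equal allocation of all 6,500 and no losses. The second uses the 4,000 that section 7.1 requires in the analysis.

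Power = Φ[(d − 1.96·se0)/se1], where d is the visible difference, se0 the pooled and se1 the unpooled standard error. For c = 1 and 3,250 per side: d = 0.012, se0 = √(2 × 0.03 × 0.97/3250) = 0.00423, se1 = √((0.024 × 0.976 + 0.036 × 0.964)/3250) = 0.00423. This gives Φ(0.876) = 81%.

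| Capture c | Visible risks | Difference (points) | Power, 3,250 per side | Power, 2,000 per side |
|---|---|---|---|---|
| 100% | 2.4% v 3.6% | 1.2 | 81% | 60% |
| 75% | 1.8% v 2.7% | 0.9 | 69% | 48% |
| 50% | 1.2% v 1.8% | 0.6 | 51% | 34% |
| 25% | 0.6% v 0.9% | 0.3 | 29% | 19% |

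The relative risk matters as much as the capture. At a relative risk of 2.0 and 2,000 per side, power is 98%, 81% and 52% at 100%, 50% and 25% capture.

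**5. The cost of asking everyone.** A broad question also picks up background complaints. Holding the excess at 1.2 points with 3,250 per side, assumed background positives of 5%, 10% and 20% give power of about 56%, 35% and 22% by the same formula.

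**The case against.** **The forms are not shown.** Appendices 8 and 10 hold the forms and Appendix 11 the outcome displays. Section 4.3 describes the purposes of the four-monthly form, not every item on it, so a symptom question may exist. This stands as a condition on the point. The text is nonetheless detailed enough to mention diabetes medication, and it mentions no symptom item.

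**Other routes exist.** A reader might infer that symptoms are recorded only when someone stops, and that people who continue are never counted. The protocol does not support that. The two-week check does not depend on stopping, admissions are collected every four months, and section 8.3 lets participants and collaborators raise worries, with concerns about side-effects relayed to the data monitoring committee. These routes can reveal cases, but none is described as recording symptoms systematically.

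**The outcome is broad and the trial is meant to be simple.** Section 6.2 promises possible adverse effects, with gastrointestinal symptoms as an example. Stopping for that reason, analysed over all randomised, is a legitimate pragmatic measure of tolerability. This stands too, and it is why relabelling is an acceptable alternative to new data collection.

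**Asking everyone may lose as much power as it gains.** The dilution figures bear this out. Blinding protects against bias but does not restore power, so a symptom item should complement the stopping measure and not replace it.

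**Conclusion.** The mismatch between sections 4 and 6.2 holds on the body text, subject to Appendices 8, 10 and 11. As written, the trial would mainly measure gastrointestinal-attributed discontinuation under the name of gastrointestinal symptoms. Absolute risk is understated. With equal capture the absolute difference is understated too, and the relative risk is roughly preserved.

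A reader might infer that the calcium comparison is necessarily biased towards no effect. It is not: if willingness to stop differs by arm, the bias can go in either direction. Nor do the documents support a definite loss of power, because the capture fraction, the 3.6% rate and the use of 2.4% as the fully ascertained risk without calcium are all assumptions.

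This is a secondary safety outcome and the primary fracture analysis is untouched. It should be corrected because the correction is cheap and the data cannot be recovered later.

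**What to change.** First check Appendix 8. If the four-monthly form already asks every participant about gastrointestinal symptoms, say so in section 4.3 and nothing more is needed.

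Otherwise, add one item to section 4.3 ii), asked of everyone whether on or off tablets: any new gastrointestinal symptoms in the preceding four months that were bothersome or led the participant to seek care. The threshold limits background reports. In section 6.2, analyse the item over all randomised and report stopping because of gastrointestinal symptoms as a separate measure.

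If no item is added, relabel the section 6.2 outcome as stopping tablets because of gastrointestinal symptoms, so that the name matches what is collected.

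The cost of the item is a slightly longer form for an elderly population, and background reports that dilute the symptom comparison; keeping the discontinuation measure alongside covers the second. Relabelling costs nothing in data collection but gives up the symptom comparison.

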6.3 Timing and frequency of analyses

A single principal analysis is anticipated two years after the last person is recruited. If considered appropriate, follow-up of recruits will be extended at this time. The data and safety monitoring committee (see below) will determine the frequency of confidential interim analyses.

6.4 Secondary sub-group analyses

Sub-group analyses similar to the principal analyses will be performed after stratification by (a) the type of fracture sustained prior to trial entry (proximal femur, distal forearm, clinical vertebral, or other), (b) age at entry (70-74, 75-79, 80-84 and 85 or over), (c) sex, (d) latitude of recruitment centre (northern versus central versus southern), (e) time of enrolling fracture (within 3 months of recruitment or longer), (f) dietary calcium (high or low) and vitamin D exposure (high or low), (g) high or low weight (less than 55kg or not), and (h) level of compliance (completed two years or not). The Chi-squared test for heterogeneity will be used to explore any apparent differential effects. The principal outcome will be subdivided into categories of fracture, again to explore possible differential effects. Stricter levels of statistical significance (2P<0.01) will be sought, reflecting the exploratory nature of all these analyses.

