6. ANALYSIS PLANS

6.1 Ground rules for the statistical analyses

The statistical analyses will be based on all people randomised, irrespective of subsequent compliance with pill taking. The principal comparisons will be:

- (i) all those randomised vitamin D versus all those not allocated vitamin D
- (ii) all those randomised calcium versus all those not allocated calcium
- (iii) all randomised vitamin D and calcium versus all randomised Vitamin D alone versus all randomised calcium alone versus all randomised placebo

Evidence will be sought for an interaction between vitamin D and calcium.

The analyses will be based on two denominators:

- (i) all participants with data irrespective of length of follow-up, using 'time to an event' and multidecrement life-table analysis techniques
- (ii) all those with follow-up to 24 months

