7. SAMPLE SIZE AND FEASIBILITY

7.1 Sample size sought

The aim is to recruit about 6,500 people to the trial. This is based on a wish to identify a reduction of one fewer person per hundred allocated an active treatment sustaining a fracture each year over a median period of three years, if this was the true effect. Based on data from published trials in similar contexts the anticipated all fracture rate in the control groups is 15%. A total of 4000 participants would be needed in the analysis to have 80% power (2P<0.05) to detect an overall reduction to 12%. If the true effect is somewhat larger, say a 4% absolute benefit, the power will be over 90%. A trial of this size also has over 80% power to identify a 2% absolute difference in hip fracture rates (from 6% to 4%, or 5% to 3%).

The numbers sought have been inflated to 6,500 to take account of losses to followup. The main reason for 'loss to follow up' will be death. In the large Dutch trial¹² the rate was about 20% over three years, but we expect it to be higher overall (about 30%) because some of our participants will have sustained a recent proximal femoral fracture. Losses for other reasons, principally moving to other areas, are estimated from observations in one participating centre to be about 5%. The sample size has therefore been inflated by 35%.

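### Section 6.4 treats two-year compliance, a post-randomisation variable, as an ordinary sub-group factor, so its within-stratum treatment comparisons are liable to selection bias

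*Protocol*

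**What the plan says.** Protocol section 6.1 sets the ground rule: "The statistical analyses will be based on all people randomised, irrespective of subsequent compliance with pill taking".

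Section 6.4 then states: "Sub-group analyses similar to the principal analyses will be performed after stratification by" eight factors. Factors (a) to (g) are enrolling fracture type, age, sex, latitude of centre, time since the enrolling fracture, dietary calcium and vitamin D exposure, and weight. All are fixed at or before entry. Factor (h) is "level of compliance (completed two years or not".

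One method covers the whole list: "The Chi-squared test for heterogeneity will be used to explore any apparent differential effects". One caveat covers it too: "Stricter levels of statistical significance (2P<0.01) will be sought, reflecting the exploratory nature of all these analyses". Nothing marks (h) as different in kind from (a) to (g).

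Compliance is collected after entry. Under section 4.3 the four-monthly form asks about the preceding week: "whether the tablets have been taken, how often, and reason for stopping if applicable".

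**The concern.** Randomisation makes the arms comparable within levels of a variable fixed before allocation. It does not do so within levels of a variable that allocation or outcome can change. Completing two years is of the second kind, and the protocol itself suggests the routes:

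- **Allocation to stopping.** Section 6.2 lists gastrointestinal symptoms as a possible adverse effect. Section 8.3 cites them in 93 of 3,892 people (2.4%) in the systematic review, not split by arm.
- **Outcome to stopping.** Section 6.5 expects some participants to enter long-term care because of a fracture, which could plausibly interrupt tablet taking.
- **Death.** Section 7.1 expects about 30% to die. Anyone who dies before month 24 cannot have completed two years.

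If such routes act unequally in the two arms, completers on active tablets and completers on placebo are differently selected groups. A difference in fracture risk between them could then appear although the tablets do nothing. Because (h) is pre-specified as an ordinary sub-group, such a difference could be read as a genuine effect modification.

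**Working it through.** **1. What the plan gives.** There is no figure for compliance or for stopping by arm. Two figures from section 7.1 are used for scale.

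- Control fracture rate: "the anticipated all fracture rate in the control groups is 15"%.
- 4,000 participants analysed. This reproduces. For 15% v 12%, two-sided 0.05 and 80% power, n per arm = [1.96√(2×0.135×0.865) + 0.842√(0.15×0.85 + 0.12×0.88)]² / 0.03² = 2,036, or 4,072 in total. With 2,000 per arm the power is 79.3%.

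Everything else below is assumed, to show whether and how bias can arise. The true relative risk (RR) is 1 throughout.

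**2. Model A: active tablets make more frail people stop; fracture does not affect stopping.** Assumed: 40% frail; fracture hazard 0.09 per year in the frail and 0.03 in others; stopping 45% in the frail and 30% in others; active tablets add d points in the frail only.

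Three-year risks are 1 − exp(−0.27) = 0.2366 and 1 − exp(−0.09) = 0.0861. Overall: 0.4×0.2366 + 0.6×0.0861 = 14.6%, close to the protocol's 15%.

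Risk in completers = Σ(share × completing × risk) / Σ(share × completing). For d = 15:

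- Control: (0.4×0.55×0.2366 + 0.6×0.70×0.0861) / 0.64 = 0.1378
- Active: (0.4×0.40×0.2366 + 0.6×0.70×0.0861) / 0.58 = 0.1276
- RR = 0.93

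In non-completers the same sum gives 0.1721 / 0.1613 = 1.07.

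| Extra stopping in the frail | RR, completers | RR, non-completers |
|---|---|---|
| 0 points | 1.00 | 1.00 |
| 2.4 points | 0.99 | 1.01 |
| 5 points | 0.98 | 1.02 |
| 10 points | 0.95 | 1.05 |
| 15 points | 0.93 | 1.07 |

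The 2.4-point row treats the whole gastrointestinal rate as excess stopping.

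**3. Model B: fracture can also cause stopping.** Assumed: 30% frail; two-year fracture risk 20% in the frail and 5.71% in others (10% overall, which is 15% × 2/3); baseline stopping 25%; frailty adds 20 points; active tablets add s points and a fracture adds f points.

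For s = 10 and f = 30, risk in completers:

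- Control: (0.3×0.20×0.25 + 0.7×0.0571×0.45) / 0.66 = 0.0500
- Active: (0.3×0.20×0.15 + 0.7×0.0571×0.35) / 0.56 = 0.0411
- RR = 0.82

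In non-completers: 0.1750 / 0.1970 = 0.89.

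| s | f | RR, completers | RR, non-completers |
|---|---|---|---|
| 0 | 30 | 1.00 | 1.00 |
| 10 | 0 | 0.98 | 0.96 |
| 5 | 20 | 0.96 | 0.95 |
| 10 | 20 | 0.90 | 0.90 |
| 10 | 30 | 0.82 | 0.89 |

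**4. Does 2P<0.01 protect?** In the last row, with 4,000 analysed, the chance of a false benefit at 2P<0.01 is about 6% in completers and 7% in non-completers, against a nominal 0.5% in that direction.

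**5. Would the heterogeneity test react?** Take z = difference in ln RR between strata, divided by its standard error, where the variance is Σ(1−r)/(nr) over the four cells. In Model A at 15 points, z = (ln 0.926 − ln 1.067) / 0.154 = −0.92, so the test rejects at 2P<0.01 about 4.9% of the time, against a nominal 1%. It rejects about 1.4% of the time at 5 points and 1.1% at 2.4 points. In Model B with s = 10 and f = 20 both strata shift equally, so the test stays at its nominal 1% although both RRs are wrong.

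**The case against.** The strongest defence is that section 6.4 is headed as secondary, calls all these analyses exploratory and asks for 2P<0.01, while section 6.1 keeps the principal comparisons on everyone randomised. This stands as a limit on severity: no primary estimate, sample size or stopping rule depends on (h). It does not answer the point. A stricter threshold guards against chance findings among many tests, whereas selection bias moves the estimate itself.

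Second, nothing in the protocol says stopping will differ by arm, and section 8.3 anticipates very few adverse effects. This also stands. Without such a difference both strata show an RR of 1.00 under a null effect, even when frailty and fracture strongly affect stopping. A reader might infer that (h) must give biased results; the documents support only that it is liable to.

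Three other stronger readings also go beyond the text:

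- **That the heterogeneity test would present the bias as a dose-response.** A two-stratum test is not a dose-response test. In the assumed models it rejects rarely, and both strata can shift the same way.
- **That early deaths measure the bias.** At a constant hazard, 30% dead over three years means 1 − 0.70^(2/3) = 21% dead by month 24. Deaths equal across arms create no between-arm bias by themselves. On section 6.1's second denominator, those followed to 24 months, these people would presumably not be counted.
- **That completion certainly means tablets.** The wording could also mean completing follow-up. Either reading is post-randomisation, so the point does not depend on which is meant.

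**Conclusion.** The point holds in limited form. Factor (h) is a post-randomisation variable given the method meant for entry-time factors. Comparisons of arms within its strata are not randomised comparisons and are liable to selection bias, which the significance threshold does not remove.

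Under a null effect, bias requires stopping to differ by allocation. On wholly assumed inputs with such a difference, the apparent RR is about 0.82 to 0.99 in completers and 0.89 to 1.07 in non-completers when the true value is 1. The direction in non-completers changes with the mechanism assumed, and at small differences in stopping the bias is slight. Neither size nor direction can be fixed from the protocol. Frailty shares, stopping rates and their dependence on fracture are all assumptions; only the overall fracture level and the 4,000 analysed are tied to section 7.1.

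This should be fixed, but it is not critical, because the principal analysis of all randomised participants is untouched.

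**What to change.** Remove (h) from the list in section 6.4 and from its heterogeneity test. If compliance is of interest, describe it in a separate paragraph as a non-randomised exploratory analysis, and say whether completing two years refers to tablets or to follow-up.

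Optionally, add a complier-average estimate with allocation as the instrument, which keeps the comparison of randomised groups. It would need a stated definition of a complier and a stated exclusion restriction, which is doubtful for people who took tablets for part of the period. It would also have to handle two factors and deaths. The data are thin for this: section 4.3 records only the preceding week, and tablet counts cover a 5% subsample.

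The cost is one fewer listed sub-group and, if the complier-average estimate is added, a wider interval than a naive compliers-only comparison. No sample size, power or significance level changes.
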